1.1 Introduction

Advanced age, frailty, comorbidity and physical inactivity are often present in patients with ischemic heart disease (IHD) awaiting coronary artery bypass graft surgery (CABG) surgery.¹ These characteristics, as well as the physiological impact of having surgery are significant homeostatic disturbances where patients postoperatively suffer from physical symptoms and a lack of a return to independence.^{2,3} Cardiac surgery invariably induces varying degrees of physiological stress, impacting multiple organ systems, and imposes psychological burden.⁴ As increasing age, patient complexity and comorbid burden grow more common in patients undergoing cardiac surgery, innovative strategies are required to alleviate the risk of adverse outcomes.⁵ Strategies to improve outcomes from surgery and accelerate return to baseline levels have traditionally focused on the intra-and postoperative period, nevertheless the waiting period before surgery might offer an opportunity for improving the safety and outcome of the surgical intervention and improve patients' motivation in postoperative rehabilitation and recovery time.^{6,7}

1.2 Background

IHD constitutes a significant cause of mortality and morbidity globally, and accounts for over four million deaths annually in Europe, placing a great strain on healthcare resources.^{8,9} In Denmark, cardiovascular diseases account for the death of one in five individuals, representing the second leading cause of mortality in the country.^{10,11} Specifically, IHD was the predominant cardiovascular disease leading to death among Danes in 2021, with an estimated 12,000 deaths attributed to cardiovascular diseases each year.¹² The prevalence of IHD escalates with advancing age and is notably higher in men compared to women, including within the elderly population. In Denmark, approximately 163,000 individuals are currently living with IHD, and approximately 12,000 new cases are diagnosed annually.¹³ The economic burden of IHD is substantial, with annual costs for treatment, care, medication, and lost productivity estimated at approximately 5.5 billion DKK.^{14,15} IHD results from atherosclerosis in the coronary arteries, reducing blood flow to the heart muscle. This condition, also known as coronary artery disease (CAD), causes arterial narrowing, which can lead to angina, blood clots, and myocardial infarction (AMI), commonly known as a heart attack.¹⁶ Diabetes, hypertension, and dyslipidemia are known to be major cardiovascular risk factors influenced by unhealthy lifestyle behaviors such as smoking, alcohol consumption, physical inactivity, and a diet high in calories and trans-fat acid. Smoking known as one of the main risk factors for developing IHD causes every year 3000 new cases of IHD in Denmark.¹⁷ An unhealthy lifestyle plays a fundamental role in the development of cardiovascular disease (CVD), requiring emphasis and attention,¹⁸ while impacting both health outcomes and quality of life. Importantly, these risk factors are modifiable, offering substantial potential for reducing CVD risk through both primary and secondary prevention strategies.⁹ Standard treatment in multivessel disease

in patients with IHD is revascularization by coronary artery bypass graft (CABG) surgery, a well-recognized, treatment to relieve symptoms of angina, improve exercise capacity, quality of life and survival.^{19,20} In 2021 a total of 1195 isolated CABG-procedures were performed at the four heart surgery centers in Denmark.²¹ Out of these were 580 carried out at The Department of Cardiothoracic Surgery at Rigshospitalet, either as an elective or acute procedure.²² CABG is acknowledged as “state of the art,”^{23,24} and is one of the most frequently performed cardiac surgeries in the Western world associated with better long-term survival compared to PCI in most regions in the world.²⁵ Despite advances in surgical techniques, anesthesiology and perioperative care⁴ postoperative complications, including infections, hemorrhage, arrhythmias, graft failure, atrial fibrillation, pneumonia, renal injury, and cerebrovascular events, are associated with an elevated risk of both early and late mortality and all-cause rehospitalization, particularly within 90 days of CABG.²⁶

1.2.1 Waiting for elective CABG surgery

Most patients scheduled for elective CABG surgery wait at home and undergo little or no physical training or other interventions in the lead up to their operation. Evidence shows that patients deteriorate functionally and psychologically during this period prior to surgery.^{1,27} Furthermore, studies show that the time spent waiting for cardiac surgery is a period of great uncertainty for the patient. There appears to be heightened anxiety regarding physical activity, mainly because of their current cardiac conditions or diagnosis.^{27,28,29} Subsequent physical inactivity characterized by sedentary behavior and lifestyle may add to the underlying IHD and this has been recognized as one of the coronary artery disease’s major risk factors.³⁰ In line with this results from the Heart Centre’s cross-sectional study conducted in the fall of 2018 and 2019, involving 130 hospitalized cardiac surgery patients, reported low activity level during the four weeks preceding their surgery indicating sedentary lifestyle in the weeks leading up to their cardiac surgery.³¹ Studies show that a decrease in physical activity quickly leads to a decline in physical fitness and reduces the physiological capacity to withstand the side effects of surgery.^{27,32} Studies show that ischemic heart patients awaiting surgery often have difficulty maintaining a normal level of physical activity, which in turn leads to reduced oxygen uptake and loss of muscle mass.³⁰ Symptoms such as fatigue, shortness of breath, and fear of angina pain can prevent the patient from being physically active.^{28,29} Additionally, anxiety and depression can contribute to reduced motivation to be physically active during the waiting period before surgery.²⁸ Moreover, resent research revealed that the prevalence of sarcopenia in older patients at cardiac rehabilitation (CR) after cardiac procedure is high (35 %), and remains high at follow-up (23%) and indicates correlations with poor functional capacity.³³ Ensuring that patients are in optimal nutritional health before undergoing CABG surgery is crucial, as it is an important driver for clinical outcomes in this population. Malnutrition, defined as an unintended nutritional intake imbalance (not necessarily a decreased intake),

is evident in 20 % of patients before cardiac surgery associated with increased morbidity and mortality.^{34,35} Malnutrition before surgery has been associated with longer length of stay (LOS) in the intensive care unit (ICU) and higher rates of postoperative cardiovascular and infectious complications.^{36,37} Further smoking and alcohol overconsumption are well known risk factors for a complicated recovery after CABG-surgery including delayed wound healing, pulmonary complications, and mortality.³⁸ Moreover preoperative alcohol abuse and misuse are likely causes of subclinical myocardial dysfunction, immunosuppression, and decreased hemostasis – increasing the risk of hemodynamic instability, infection, and bleeding.^{39,40}

1.2.2 Recommendation and guidelines

The adoption of routine preoperative optimization strategies for patients awaiting CABG surgery has so far been limited although the Health Authority's "Recommendations for Cross-Sectional Pathways for People with Heart Disease," suggest that the multi-disciplinary team (MDT) conference's conclusion should also include a plan for preoperative preparation to improve postoperative outcomes and increase rehabilitation potential.⁴¹ In Denmark, patients have historically been waiting weeks for heart surgery but it fluctuates. Patients are called for heart surgery approximately two to four weeks before, where they either remain hospitalized or are discharged home during the waiting period. The patient receives written informational material about the process before and after CABG surgery. For patients who are fully examined and referred for CABG surgery, there will be an intermediate period. In this period it is recommended that the patient is prepared for the procedure and that the rehabilitation potential is strengthened through physical activity, thereby reducing the loss of function before subsequent rehabilitation. In addition to optimization of medication and chronic conditions, patients should be offered, smoking and alcohol cessation, nutritional support, and physical training according to individual need.⁴¹

Evidence suggest smoking cessation at least four weeks before CABG surgery reduces the risk of major postoperative pulmonary complications such as reintubation, atelectasis and pneumonia.⁴² The recommendations by The Danish Health authority is smoking cessation six weeks before surgery.⁴³ Similar to smoking cessation, abstinence from alcohol is not treated as a prerequisite for surgery, but recommendations from the Danish Health Authority recommend zero alcohol intake four weeks before surgery.⁴⁴ The European Society for Clinical Nutrition and Metabolism guidelines recommend an increased intake of protein before surgery to reduce the physiological stress response after surgery.⁴⁵

1.2.3 Prehabilitation in patients with IHD awaiting elective CABG surgery.

Prehabilitation is a newly introduced term that reflects a proactive process of enhancing an individual's functional capacity between diagnosis and scheduled surgery, intending to improve the patient's capacity to withstand the upcoming physiologic stress of surgery and thus avoid complications.⁴⁶ This period of awaiting

surgery is proposed as a “window of opportunity” to address poor nutritional status, low physical fitness, and high emotional distress.^{47,48} The role of multimodal prehabilitation combining exercise training, nutritional optimization, and psychological support, in patients with IHD awaiting CABG surgery is sparse⁴⁹ and unknown in a Danish setting. We conducted a scoping review⁵⁰ of prehabilitation in elective CABG surgery patients in accordance with JBI methodology for scoping reviews,^{51,52} in May 2023. We updated the systematic literature search in Medline (PubMed), Embase (Ovid) and Cochrane Central in February 2024 to identify new studies on the topic. This scoping review⁵⁰ examined prehabilitation interventions to optimize outcomes after elective CABG surgery and found that available evidence is mostly based on small studies with high heterogeneity. Prehabilitation before CABG-surgery has been described as a combination of exercise training, education, and social support affecting patients’ physical and psychological readiness for surgery intended to reduce postoperative complications and LOS.^{6,53,54} To ensure that patients undergoing elective CABG surgery benefit from prehabilitation, there is a need for methodologically rigorous clinical trials and comprehensive knowledge synthesis. These efforts are necessary to identify optimal strategies for patient selection, intervention design, adherence, and the duration of interventions.⁵⁰ Additionally, existing evidence indicates that prehabilitation programs should be tailored and centered around individual patient needs.⁵⁵ Recently a meta-analysis examining the effects of exercise-based prehabilitation in cardiac surgery patients on various perioperative outcomes, as compared to standard care, demonstrated significantly improved post-surgery six-minute walking distance, reduced LOS, and a decreased risk of postoperative atrial fibrillation (AF) in patients aged 65 years or younger.⁷ Furthermore a systematic review confirmed improvement in functional capacity and declines in postoperative complications and LOS.⁵⁶

This support prehabilitation as integrated into cardiac surgical planning⁵⁷ towards optimizing patients before surgery and potentially enhance surgical outcomes. However, it also concludes that the ideal prehabilitation regimen remains uncertain, particularly in terms of the significance of dietary modifications and psychological preparations for surgery, the benefits of which are not yet fully understood in cardiac surgical patients.⁵⁷ Nevertheless, a formalized prehabilitation program focusing on prehabilitation for cardiac surgery patients has not yet been established in Denmark. We propose that patients awaiting elective CABG surgery who receive a home-based multimodal prehabilitation intervention, in addition to usual care (UC), will show improvements in physical activity, functional capacity, mental health, and quality of life postoperatively. These improvements may also positively impact health behavior, health outcomes, length of hospital stay, and days alive out of the hospital after surgery. Additionally, as far as we know no previous studies have investigated a home-based multimodal prehabilitation intervention program within this patient population in Denmark, while recent findings in a scoping review⁵⁰ provides a comprehensive summary of strategies that will be applied when developing a prehabilitation program for patients awaiting elective CABG surgery for

optimizing physical capacity, lifestyle behaviors, mental health, and nutritional status in preparation prior to CABG surgery.⁵⁰ Before a larger randomized controlled trial (RCT) can be conducted, a feasibility study is required to determine if a larger trial is possible, and if so, outline the optimal design features.⁵⁸ It can be described as complex interventions according to the UK Medical Research Council, why conducting a feasibility study as part of the process from developing to implementation is recommended.⁵⁹

2. Study aim and objectives

This CABGpreHAB feasibility study is conducted to evaluate the feasibility of delivering a homebased multimodal prehabilitation intervention for patients awaiting elective CABG surgery with the purpose to optimize a subsequent full-scale RCT:

2.1 Primary objective

The primary objective of this feasibility study is to determine if it is feasible for patients awaiting elective CABG surgery to participate in a preoperative homebased multimodal prehabilitation intervention. We will evaluate this through completion of the following objectives:

- Assess the proportion of eligible patients that are recruited into the study.
- Assess the suitability of inclusion and exclusion criteria by examining recruitment data.
- Explore reasons for non-consent to study participation.
- Assess the acceptability of the study to patients by measuring recruitment and retention to the study and thorough qualitative interview responses.
- Assess the acceptability of the intervention through qualitative interviews and retention rates during the study.
- Assess adherence to and completion of the intervention (i.e. do participants adhere and work through all components of the intervention) and explore engagement and satisfaction with the interventions by qualitative interviews.
- Assess the proportion of patients lost to follow-up after study entry.
- Assess safety of the interventions.
- Explore the appropriateness of outcome measures, completion rates and assess response to questionnaires through qualitative interviews.
- Evaluate the logistics of delivering a home-based tele-exercise training intervention through qualitative interview responses from both health care professionals and patients.
- Determine the “prehabilitation window” (length of time between MDT-conference and CABG surgery)

2.2 Secondary objective:

The secondary objectives will evaluate if the multimodal prehabilitation intervention has an impact on preoperative and postoperative outcomes. For this we will collect data on study outcomes to assess levels, variation, and changes over time, which can inform sample size for the future RCT, as shown in **Table 1**, section 7.2.

3. Method

[figure not shown]
3.1 Study design

The CABGpreHAB feasibility study is designed as a randomized pilot study, aiming to assess the feasibility of a multimodal prehabilitation intervention plus usual care versus usual care alone in patients awaiting elective CABG surgery. It is an investigator-initiated study designed as an open-label, single-center randomized controlled feasibility study (allocation ratio 1:1) with blinded outcome assessment, designed to assess the method proposed for use in a larger RCT. This protocol follows guidance from Standard Protocol Items: Recommendations for Interventional Trials (SPIRIT).⁶⁰ The CABGpreHAB study will be registered at www.ClinicalTrials.gov before initiation.

3.2 Inclusion and screening procedure

Patients referred to elective CABG surgery who are deemed eligible due to inclusion criteria will be identified and assessed for eligibility by the responsible surgeon after the MDT-conference as shown in **Figure 1**.

Figure 1. CONSORT⁶¹ diagram to illustrate flow of participants through the study.

3.3 Randomization

Following baseline assessment, randomization will occur in a 1:1 ratio, stratified by age, gender (men, women), and EuroSCORE (indicative of disease severity), assigning participants either to the intervention group or to usual care. Randomization is completed using the web-based tool Randomizer for Clinical Trials.

3.4 Blinding

Due to the nature and conditions of prehabilitation, the interventions are open, making it impossible to blind the interventions to the staff and patients.⁶¹ However, all physical testing, data collection, and administration will be conducted by blinded staff. Statistical analysis of outcomes and the conclusions derived from these analyses will also be performed in a blinded manner. The study results will be analyzed by an independent statistician, and the research group will interpret the results. The conclusions will be prepared in two versions before the allocation code is broken, with each version assuming alternately that one arm is the intervention: one version will assume that arm A is the intervention, and the other will assume that arm B is the intervention.

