6.2.1 Exercise intervention

During the initial assessment patients will be taught how to perform the exercises to complete at home during the intervention period. The exercise intervention is supervised by skilled physiotherapists and delivered via Infinity Connect app and a webcam⁷² at Rigshospitalet to a group of approximately 4–8 patients who exercise at home and communicate via a tablet. Each session is 60 min, i.e., 40 min of exercise and 20 min of patient education, three times per week for the prehabilitation period. The exercises used in the program are identified and selected amongst exercises used in previous exercise intervention studies and involves larger muscle groups with 50/50% exercises for upper and lower extremities, respectively.⁷³ The exercises are executed in four sets to achieve peripheral muscle fatigue and secondary dyspnea/breathlessness. Each set is carried out in a predefined period of 20 to 40 s with a maximum number of repetitions performed, i.e., 8 to 25 repetitions depending on the patients exercise capacity and motivation, but with the aim of 12 to 20 repetitions.^{73,74} In practice the training intensity is determined by using the self-rated Borg Scale, moderate intensity RPE 11-15, 50-60% VO₂peak.⁷⁴

The first week serve as a familiarization phase with the purpose to adapt to exercising, adjusting, and optimizing load and to avoid musculoskeletal overload injuries. Monitoring physical activity and providing motivation through phone calls weekly will be enhanced by incorporating a novel accelerometer system, offering activity level feedback (SENS innovation)⁷⁵ to guide healthcare staff. Participants in the intervention will be instructed to perform daily exercise tasks such as brisk walking and sit-stand exercises. Additionally, motivational phone calls will be made to participants in the intervention group, while healthcare staff will receive feedback on these patients, aiding to guide them in achieving their activity goals. Patients will also be asked to complete a diary describing physical activity outside the programmed session, included in a patient booklet. All study participants will wear the accelerometer from the screening phase until the day preceding the procedure, and again postoperatively until the day of discharge and for 30 days

thereafter.^{76,77} The technology platform provided to the patients includes a tablet and an accelerometer device to facilitate exercise training sessions and data collection.

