Safety: Safety of the intervention will be determined based on the number and nature of adverse events (AE), which is defined as any discomfort or symptoms of angina pectoris that will prevent a patient to take part in the physical tele exercise sessions or symptoms that require medical attention. Adverse event (AE), serious AE (SAE), serious adverse reaction (SAR), and suspected unexpected serious adverse reaction (SUSAR) will be monitored during the trial counting the number of occurrences. In addition to the physiotherapist

taking note of any undesirable effect during and after the tele session or phone counselling with the project nurse, all participants are asked to report any symptoms that was not consistent with their usual physical condition presentation as a result of exercise sessions.

For a lager RCT trial to be deemed feasible, feasibility outcomes need to be attained, meaning that more than 60% of eligible patients will participate and at least 52% of the intervention group will receive more than 60% of the intended interventions.⁸⁷

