Sit to stand (fysisk fridly)		X		X			X*
SENSE® Daily activity score		X		X		X	X
Copenhagen City Heart study		X					
SF-12 (HRQoL)		X		X			X
HeartQoL (Heart-specific QoL)		X		X			X
STATE-Anxiety + Trait-anxiety (baseline only)		X		X			X
PHQ -4		X		X			X
SOC-13		X					
PAM ₁₃		X		X			X
Tobacco uses status		X		X			X
Alcohol use status		X		X			X
Adverse events			X				
Other Outcomes							
PO complications ³							X
ICU -LOS /LOS							X
DAOH ₃₀							X
Participating in CR							X
Hgb, Albumin, CRP, creatinine		X				X	

¹ Euroscore II, LVEF, NYHA class, BMI, height

² Age, gender, marital status, occupational status, educational level,

³ AF, re-operation, pneumonia, delirium, deep sternal infection, stroke. *Test foretages enten på Rigshospitalet eller lokalt på hjemsygehus.

Abbreviations: DAOH₃₀: Days alive and out of hospital; CR: Cardiac rehabilitation; PO: postoperative; AF: Atrial fibrillation; ICU-LOS: intensive care unit length of stay; LOS: length of stay; NRS-2002: Nutrition Risk Screening; PAM₁₃: Patient activation measures; PHQ-4: Patient Health Questionnaire; SOC-13: Sense of Coherence-13.

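### Section 3.4 claims blinded staff for all data collection, but session adverse events and adherence come from unblinded treating staff in one arm, so pooled adverse event counts are not comparable between arms

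*Protocol*

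**What the plan says.** Section 3.1 describes an open-label, "single-center randomized controlled feasibility study (allocation ratio 1:1) with blinded outcome assessment". Section 3.4 concedes that "the interventions are open, making it impossible to blind the interventions to the staff and patients", and then asserts without exception that "all physical testing, data collection, and administration will be conducted by blinded staff".

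Section 7.1 lists adherence and safety among the primary feasibility outcomes.

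- **Safety, source.** The physiotherapist is described as "taking note of any undesirable effect during and after the tele session or phone counselling with the project nurse". All participants are also asked to report unusual symptoms, but only those arising from exercise sessions.
- **Safety, definition.** Section 7.1 defines an adverse event in two parts. The first is "any discomfort or symptoms of angina pectoris that will prevent a patient to take part in the physical tele exercise sessions"; the second is symptoms needing medical attention. Section 10.2.1 defines it as any undesirable medical event in a participant, whether or not the intervention caused it.
- **Adherence.** Session counts in the intervention group are taken from a patient logbook, weekly telephone calls and the accelerometer.

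Table 1 and section 8.2 give the patient record as a source of adverse events during the intervention period. Section 8.2 has records read by study personnel, and section 10.2.4 has events registered by a project employee. Neither section says that these people are unaware of allocation.

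**The concern.** An unqualified statement that blinded staff collect all data will be read, and probably repeated in the trial report, as a property of every outcome. For two primary feasibility domains the protocol's own procedures show otherwise.

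The safety domain has a further difficulty. If one arm is observed at several scheduled contacts a week and the other only through the patient record, more events will be found in the first arm even when the true rates are equal. A table of all recorded adverse events by arm would then partly measure how hard each arm was watched. This study is meant to shape a full-scale trial, so a distorted safety description could be carried into its design and patient information.

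**Working it through.** The protocol gives no figure to reproduce here: no adverse event rate, detection rate or safety threshold is stated. The check is mainly a comparison of sections, with a count of contacts.

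**1. Who collects what**

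| Data | Collected by or from | Arm | Fits the 3.4 claim? |
|---|---|---|---|
| Physical tests | Blinded staff (3.4) | Both | Yes; nothing contradicts it |
| Session adverse event notes | Physiotherapist delivering the session (7.1) | Intervention only | No |
| Adherence by weekly call | Staff making the intervention calls (7.1, with 6.2.1 and the end of 6.2.5) | Intervention only | No |
| Adverse events from records | Study personnel or a project employee (8.2, 10.2.4) | Both | Not stated |

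The third row rests on an inference: section 7.1 does not say who makes the adherence call. The weekly calls described elsewhere are the motivational calls (6.2.1) and the nurse's counselling (end of 6.2.5), and both are part of the intervention.

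**2. How much extra observation**

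Inputs: three web sessions and one nurse call per week (end of 6.2.5); a wait of at least two weeks (4.1); a 30-day recommended maximum wait (10.3.1).

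Scheduled contacts = (3 + 1) × days / 7

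- 14 days: 4 × 2 = 8 (6 sessions, 2 calls)
- 30 days: 4 × 30/7 = 17.1 (12.9 sessions, 4.3 calls)

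The sentence naming the note-taker can be read as covering the sessions only. On that narrower reading the counts are 6 and 12.9. The control arm has none of these contacts on either reading.

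**3. Whether the definition is neutral between arms**

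The first part of the 7.1 definition requires a tele-exercise session to be prevented, so a control patient cannot meet it. The self-report request reaches everyone but asks about effects of sessions that controls do not attend. The part on medical attention, and the whole of the 10.2.1 definition, can be met in either arm. The protocol therefore carries two definitions that would give different counts, and one of them is partly arm-specific.

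**4. What unequal detection could do (assumed values)**

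Expected recorded events per arm = 25 × true risk × detection probability, with 25 per arm from section 3.6. Assume a true risk of 20% in both arms and detection of 0.9 in the intervention arm:

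| Control detection | Intervention | Control | Apparent ratio |
|---|---|---|---|
| 0.9 | 4.5 | 4.5 | 1.0 |
| 0.7 | 4.5 | 3.5 | 1.3 |
| 0.5 | 4.5 | 2.5 | 1.8 |
| 0.3 | 4.5 | 1.5 | 3.0 |

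The ratio is the quotient of the two detection probabilities, so it is the same at true risks of 10% or 30%. The detection values are not in the protocol. The table shows a possible distortion, not an estimated one.

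**The case against.** The strongest reply is that no comparison of adverse events between arms is planned. Section 7.1 judges the safety of the intervention by the number and nature of events, section 9.1 reports them descriptively, and the progression rule in 7.1 uses only recruitment and receipt of the intervention. Close watching of patients who are exercising is proper when the question is whether the exercise is safe. Controls are covered by the patient record, and recording adherence in one arm is inherent and no bias in itself.

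Most of this stands, and it limits the consequence: no test is invalidated and no go/no-go threshold depends on adverse events. It does not rescue the unqualified sentence in 3.4, and it does not make counts that mix session notes with record review comparable across randomised arms.

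A reader might also infer more than the documents support:

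- **Questionnaires.** That patients know their arm is disclosed in 3.4. The claim there concerns staff.
- **30-day tests at local hospitals.** The Table 2 footnote, "Test foretages enten på Rigshospitalet eller lokalt på hjemsygehus", allows local testing, but nothing says that local testers know the allocation.
- **Accelerometer feedback.** The statement in 6.2.1 that "healthcare staff will receive feedback on these patients" describes delivery of the intervention, not outcome assessment.
- **Blinded analysis.** Section 3.4 says that "Statistical analysis of outcomes and the conclusions derived from these analyses will also be performed in a blinded manner". Adherence and session files would reveal which arm is which, but the protocol does not say they are released before the coded-arm analysis is complete. That order can properly be set in a statistical analysis plan not seen here.

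**Conclusion.** The point holds in a limited form. The blinding sentence in section 3.4 is contradicted by section 7.1 for session adverse events and, on the most natural reading of who makes the weekly calls, for adherence. Adverse event ascertainment is unequal by design: 8 to about 17 extra scheduled contacts in one arm (6 to about 13 if only sessions count), with a definition partly tied to those contacts and at odds with section 10.2.1. Pooled counts by arm would therefore not be comparable. The size of the distortion cannot be derived from the protocol.

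It would go too far to say that controls have no adverse event ascertainment, that physical testing is unblinded, or that a planned test fails. The harm is an overstated blinding claim and a potentially misleading safety description. Both are worth correcting before the study reports, because safety is one of its primary feasibility outcomes.

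**What to change.** 1. In section 3.4, limit the blinding claim to physical testing and to any record abstraction actually done by staff unaware of allocation. State who abstracts the records and whether they are blinded, since sections 8.2 and 10.2.4 leave this open. Name session adverse event notes and adherence data as unblinded, and align section 3.1.
2. Reconcile the adverse event definitions in sections 7.1 and 10.2.1.
3. In sections 7.1 and 9.1, set out adverse events by arm only from the patient record, using the arm-neutral definition in 10.2.1. Report session-noted events in a separate table, labelled as intervention-arm data.

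The cost is rewording of these sections, a weaker stated blinding claim and one extra table. No additional visits, patients or data collection are needed.
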